**Table 3.6. Thermal effects of laser radiation**

| Temperature | Biological effect                                     |
|-------------|---|
| 37°C        | Normal  |
| 45°C        | Hyperthermia  |
| 50°C        | Reduction in enzyme activity,
Cell immobility      |
| 60°C        | Denaturation of proteins and collagen,
Coagulation |
| 80°C        | Permeabilization of membranes                         |
| 100°C       | Vaporization,
Thermal decomposition (ablation)     |
| > 150°C     | Carbonization   |
| > 300°C     | Melting   |

The same volume shows a curve that links the duration of the thermal stimulus with the reversibility of the process induced by this stimulus.

[figure not shown]

Fig. 3.21. Critical temperatures for the occurrence of cell necrosis. Data according to Henriques (1947) and Eichler and Seiler (1991)

This data on the physiological effects of temperature was the first constraint for the definition of treatment parameters.

In addition to studies related to the influence of temperature, the decision of treatment time is based on a finite element model (14) which correlates optical power, treatment time and final temperature induced by the treatment with the device in question. The initial model led to establish the conditions of optimal work, that were then tested in an animal model study.

The animal study, as reported in the article, allowed us to verify the effectiveness of the treatment sized this way relatively to the standard on an abrasion-induced wound with mechanical abrader on the back of the animal. The observations that were made showed the absence of thermal damage in the areas adjacent to the wound and confirmed that only one treatment is sufficient to trigger and accelerate the process of wound healing.

The mechanisms described above are in line with what is directly observed in a preclinical study on animal model, which is part of the Lightpatch project in the context of the BiophotonicPlus call 2012, where a fiber-optic version of the Emoled device was used to treat injuries caused by abrasions on the back of CD1 albino male mice.

Previously, two clinical studies on acute lesions (skin sampling areas) were carried out, along with two studies on chronic injuries, one of them currently in progress. The first study performed with Emoled v.0 devices (completely analogous to the v.1 devices regarding the type of energy and power emitted) was performed on 20 patients afferent at the Great Burns Centre AOUP - Santa Chiara Hospital in Pisa. The collection areas were divided into two not bordering sub-areas of the same size (10x10 cm), one of which treated only with standard therapy – or application of dressing and bandage - while the second was treated with Emoled for 30 seconds immediately after skin exportation. The results showed, in the 15 days of observation, a tendency to heal faster in the treated area compared to the control area.

The second study was carried out on 20 patients belonging to the Santa Maria Annunziata Hospital in Ponte a Niccheri - regional reference center for melanoma - in Florence. Again, patients needed an autologous skin transplant, but they were not hospitalized, so they went to the clinic for a visit every 3 days for the 15 days of observation.

The analyzes show a trend towards faster healing in the areas treated with Emoled compared to the untreated ones: considering the healing time and the post-operative course it seems significantly faster for the areas treated with Emoled compared to those treated only with standard dressings.

The third multicenter study was performed on chronic leg ulcers with a wound presence of at least 8 weeks. The study involved the enrollment of 90 patients who have two wounds, one of which was used as a control wound, or had only one particularly large wound, which is only half treated with Emoled. Enrolled patients were followed up on an outpatient basis for 10 weeks. The results significantly demonstrate that wounds or parts of wounds treated with Emoled had a higher mean re-epithelialization at week 10 than wounds treated with standard dressings only. The 10-week healing trend is also significantly higher in wounds treated with Emoled. The pain trend measured with the VASS scale undergoes a significant reduction already starting from the fourth week of treatment. The study shows in particular the efficacy of the device under study in venous type ulcers. A further multicenter clinical study is currently underway with the Emoled device which plans to observe patients with venous or mixed wounds over a period of 16 weeks. This trial is aimed not only at demonstrating therapeutic efficacy and safety, but also improving the quality of life of patients and the cost/benefit ratio for society and for health.

In this study the control group -of patients who go to the clinic twice a week and the treated group of patients treated with Emoled who visit once a week receiving blue light application in addition to standard treatment are compared. In this case, no data are yet available as enrollment is at 30% and only a small number of patients completed the study. However, no expected or unexpected side effects or device-related adverse events were found.

In conclusion, since no adverse event or side effect have been recorded and since the wounds treated with Emoled healed faster and better than the control wounds, the risk-benefit ratio is assessed clearly shifted towards the Emoled treatment. Even in clinical practice, since 2018, no adverse events or side effects have occurred in facilities that use the device, and its efficacy in different types of ulcers has been confirmed (20, 21).

### **Study Objectives**

This is a pilot case / control clinical study on a group of outpatients with diabetic foot lesions aiming to verify the efficacy and safety of the Blue light photobiomodulation therapy with Emoled medical device, in addition to standard therapy compared to the standard therapy alone, evaluating the percentage of healed lesions (which have reached complete and lasting re-epithelialization), the assessment of the healing time and reduction of the ulcerated area, the perception of pain and the quality of life of the enrolled patients.

The aim of this study is therefore to determine any differences in outcome between the two considered groups and, in particular, if the therapy of the Emoled group is more effective than the standard therapy in terms of healing rate of lesions, healing time and reduction of the ulcerated area, pain perception and quality of life, and if is at least as safe in terms of occurrence of adverse events. Furthermore, another objective is to assess the economic impact of the two treatment options in the two groups.

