Despite a dedicated organization, in 55-66% of cases the duration of diabetic foot ulcers (DFU) is not known, or the diagnosis is delayed by more than 3 weeks from the appearance of the ulcer. The delayed sending of acute DFUs carries a high risk of amputation (about 50% of total amputations affect diabetic patients). Guidelines and protocols are often not recognized and followed: 30-40% of general practitioners consider the management of DFUs unclear for the absence of Standards of Care and specific paths.

The availability of podological clinics in the Anti-diabetes Centers in Italy is still not homogenous and most of the Centers does not present the professional figure of the podiatrist within the multidisciplinary team.

This clinical trial will be a prospective, single-center, randomized controlled parallel group, superiority study with the commercial objective of evaluating the clinical efficacy of a battery-powered portable device that uses blue LEDs. The study aims, over the planned observation weeks, to clinically compare two groups of patients with neuro-ischemic foot lesions in patients with type I or II diabetes. The aim is to determine any differences in outcome between the two groups that are considered and whether the therapy of the treatment group is a valid alternative to current therapy in terms of percentage of patients healed, speed of healing, quality of life and economic impact.

Group 1, the control group, will follow the standard treatment provided by the facility protocol with wound cleaning and adequate dressing. Group 2, the treated group, will follow the standard treatment provided by the hospital protocol with wound cleaning and adequate dressing, adding the treatment with the Emoled device, which is set between the cleansing and the application of the dressing. This treatment consists in irradiating with the blue light emitted by the device, for two minutes, each circular area with a diameter of 5 cm of the lesion, twice a week for twenty weeks.

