#### *Study secondary endpoints*

1. Healing time (in which healing is represented by a lasting and complete re-epithelialization);
2. Reduction of the lesion surface in both arms, during the 20 weeks, measured in absolute terms (square centimeters) and as % of the initial size;
3. Quality of life (QoL), evaluated both with specific questionnaires (EuroQoL-5D) and generic questionnaires (Wound-QoL);
4. Perception of pain measured with a subjective analogue rating scale (VAS);
5. Assessment of the costs related to the two arms in the perspective of the National Health System, NHS (considering only direct health costs) and in the perspective of the Society (considering beyond direct health costs, direct non-health costs and indirect costs);
6. Patient's satisfaction with the EmoLED therapy, assessed by administering specific questionnaires;
7. Appreciation, complexity and usefulness of the EmoLED therapy by the operators assessed through the administration of specific questionnaires;
8. Security of treatment (number of Adverse Events in the two groups);
9. Evaluation of the cost-effectiveness of using EmoLED for the treatment of ulcers.

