Patients will be randomized into the two arms of the study according to a list of random numbers generated by special IT tools and communicated by the scientific supervisor to the Care Provider via e-mail.

It is a 1: 1, single-block randomization of 40 patients distributed in the two groups (treated and control). After the two-week enrollment observation period, the Investigator at the outpatient center will ascertains the conditions for the study prosecution and he will notify the Head of the Care Providers to take charge of the patient included in the study and to proceed with the assignment to one of the groups. In this way, the Investigator at the outpatient center will be blinded to the treatment performed at home by the patient.

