### **Sample Size**

Since there is no reference in literature to the efficacy of the treatment under study, as this is a pilot trial, it is not possible to establish a sample size that guarantees adequate significance to the results.

Furthermore, the number of eligible patients cannot be determined a priori because, after two weeks of pre-screening, the enrolled patient could conclude the study without producing data for the endpoint analysis. At the facility involved in this clinical study, will therefore be recruited a total of 40 consecutive patients (20 per arm) who are randomized.

The estimated time for enrollment is approximately 18 months.

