### **Statistics**

#### **Sample number**

Despite the presence in the scientific literature of data on average healing times of diabetic foot ulcers, the absence of clinical experience that associates blue light treatments with the therapy of this type of lesions and the lack of reliability of any inference based on clinical studies that associate this type of treatment with other types of skin lesions, due to the different etiologies and types of patients, it is not possible to perform a reliable calculation of the sample number.

The predefined sample size was therefore set on the basis of considerations concerning the recruitment capacity of the centre involved in the project. Based on an estimate of historical clinical activity data at the Diabetology Unit, where patients will be enlisted, the number of patients with diabetic foot ulcers is about 500 patients/year of which about 35% is affected by neuroischemic ulcer.

With an average of 30% of these patients reaching a healing rate of more than 50% in the first two weeks, and a further percentage of patients being excluded at the time of recruitment based on inclusion/exclusion criteria, in 18 months of enlistment it is possible to reach a number of 40 patients compared to a percentage of drop-out/denial equal to about 25%. A total of 40 patients will be recruited, 20 patients per arm.

Thus, this study is intended as a "proof of concept", the results of which may be used as preliminary information to define the sample size in later studies.

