### **Statistical analysis**

Demographic and clinical data will be presented in tables and graphs in the form of frequencies and percentages for categorical variables, mean, standard deviation, median and interquartile range for continuous variables, differentiating by reference population and treatment group.

In the first analysis a qualitative comparison between the treatment groups will be carried out (healed/not healed) through the test  $\chi^2$  or the exact test of Fisher in the case of counts of less than 5. The results will be presented in contingency tables and bar charts.

A quantitative comparative statistic between treatment groups will then be performed by comparing the percentage reduction in the area of injury, the variation in quality of life level (QoL) and the variation in pain perception (VASS) through Mann-Whitney's nonparametric test.

The choice to perform a non-parametric analysis lies in the low sample size and therefore it is preferred to have more conservative significance values. The results will be presented in tables with median and interquartile interval in the two groups with its p.value and graphically through the box plot.

To analyze the internal and time-related differences between groups, Friedman's non-parametric test for the outcome variables will be performed.

Generalized linear models (GLM) will be used to investigate whether differences between the two groups are influenced in a confusing way by demographic, clinical covariates, pre-treatment measurement, and to measure their impact which will allow us to understand which variables they include on the outcome and will also allow us to analyze the differences between the equal groups of these covariates.

For the comparison about recovery time, since the study is based on the principle of "intention to treat" and therefore there is no caesura, it will be performed by comparing the average recovery times through the non-parametric test of Mann-Whitney.

Then a descriptive statistic will be made through tables with frequencies and percentages, and bar charts of the treatment satisfaction indices in patients and operators. In addition, adverse events in both groups will be described, if present.

Due to the generally asymmetric nature of the cost distribution, the comparison of the costs associated with the two treatment arms, both from the perspective of the SSN and the Company, will be carried out using the non-parametric U test of Mann-Whitney.

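### The aim of determining whether EmoLED is no worse than standard care on adverse events cannot be answered by a 40-patient superiority pilot that describes events by arm

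*Protocol*

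**What the plan says.** Study Objectives introduces the trial as a pilot and then sets out what it is to determine. After the efficacy outcomes it adds, of the EmoLED group's therapy, "if is at least as safe in terms of occurrence of adverse events". No qualification is attached to that clause.

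The rest of the Protocol is built differently:

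- **Design.** The Literature review and rationale section calls the trial a "randomized controlled parallel group, superiority study". No non-inferiority component is declared.
- **Endpoint.** Safety is item 8 of the Study secondary endpoints: "Security of treatment (number of Adverse Events in the two groups".
- **Analysis.** The Statistical analysis section says that "adverse events in both groups will be described, if present". It names between-group tests for healing, lesion area, quality of life, pain, recovery time and costs, but none for adverse events.
- **Size.** The Sample Size section states that "will therefore be recruited a total of 40 consecutive patients (20 per arm) who are randomized". It also concedes that "it is not possible to establish a sample size that guarantees adequate significance to the results". The Sample number section repeats that "it is not possible to perform a reliable calculation of the sample number", bases the figure on recruitment capacity and calls the study a proof of concept.

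**The concern.** To conclude that a treatment is at least as safe as its comparator, the data must rule out a relevant excess of events. Observing similar counts, or none, does not do that in a small trial. The aim therefore asks a question of a different kind from the one the design and analysis address.

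What is at stake is what the final report may say. An uneventful or similar-looking table would appear to answer the stated aim, although sizeable excess rates would remain compatible with it. The Protocol has already reasoned in this direction. Its account of earlier experience (in the section on the device's principle of operation) moves from no recorded adverse events to a risk-benefit balance clearly in favour of EmoLED. The section on incidents identifies the trial as a post-market clinical follow-up study, so a safety statement from it could be used as post-market evidence.

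**Working it through.** **The plan's own figure.** The 40 patients cannot be reproduced from a statistical formula, because the Protocol gives no effect size, power or margin and says so. The check is therefore what 20 per arm can say about safety.

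**Inputs from the Protocol.** 20 per arm, allocated 1:1 (Sample Size; Study design: "single-block randomization of 40 patients distributed in the two groups (treated and control"); significance at p < 0.05, sidedness not stated (Statistical analysis); drop-out or refusal of about 25% (Sample number).

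**Assumptions.** The Protocol gives no adverse-event rate for this population and no margin. The rates, counts and margins below are illustrative. The unit is the patient with at least one event, whereas item 8 counts events.

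**1. Upper bound when no events are seen.** If 0 of *n* patients have an event, the exact upper limit is 1 − α^(1/*n*).

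- One-sided 95%, *n* = 20: 1 − 0.05^(1/20) = 0.139, or 13.9%.
- Two-sided 95%, *n* = 20: 1 − 0.025^(1/20) = 0.168, or 16.8%.

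**2. Interval for the difference when both arms look the same.** With Wilson limits (*l*, *u*) for each arm and equal observed proportions *p*, the Newcombe 95% interval is ± √[(*p* − *l*)² + (*u* − *p*)²].

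- For 0/20, *l* = 0 and *u* = 3.84/(20 + 3.84) = 0.161, so the interval is ±16.1 points.
- For 4/20, *l* = 0.081 and *u* = 0.416, so the interval is ± √(0.119² + 0.216²) = ±24.7 points.

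| Observed in both arms | 95% interval for the difference (points) |
|---|---|
| 0/20 | ±16.1 |
| 2/20 | ±21.4 |
| 4/20 | ±24.7 |
| 6/20 | ±26.8 |

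If the whole 25% were lost after randomization (20 × 0.75 = 15 per arm, a pessimistic reading), 0/15 in both arms gives ±20.4 points and 3/15 gives ±28.3.

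**3. What a non-inferiority conclusion would need.** With equal true rates *p*, margin *m*, one-sided α = 0.025 and an assumed power of 80%, *n* per arm = (1.960 + 0.842)² × 2*p*(1 − *p*)/*m*². For *p* = 10% and *m* = 10 points this is 7.85 × 0.18/0.01, which rounds up to 142. The last column is the smallest margin with 80% power at 20 per arm, 2.80 × √[2*p*(1 − *p*)/20].

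| True rate | *n* per arm, 10-point margin | *n* per arm, 20-point margin | Smallest margin at 20 per arm |
|---|---|---|---|
| 10% | 142 | 36 | 27 points |
| 20% | 252 | 63 | 35 points |
| 30% | 330 | 83 | 41 points |

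At a 5% rate the smallest margin is still 19 points. Only a margin that is very wide for the rate comes within reach.

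**The case against.** The strongest reply is that this reads one clause too literally. The phrase occurs once, in a narrative aim. The section headed Primary and secondary objectives speaks only of safety of treatment. Study Objectives itself opens by calling the trial a pilot, and both sample-size sections disclaim inferential strength. The endpoint and analysis already describe events by group, which is a reasonable way to report safety in 40 patients. Limited precision affects the efficacy aims equally and is disclosed.

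Most of this stands and keeps the point small. It does not remove it. The disclaimers concern sample size and do not limit the safety clause, which stays unqualified.

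A reader might go further and infer three things that the Protocol does not support:

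- **That the lack of a margin, interval or counting rule is itself an error.** A statistical analysis plan, not available here, could supply these. It could not make 20 per arm precise enough.
- **That no comparison of safety is planned.** A descriptive comparison by group is planned; only an inferential one is absent.
- **That the sponsor will report absence of events as proof of equal safety.** No section sets a rule for declaring this, and no test is attached to adverse events. The aim leaves that reading open but does not commit the report to it.

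**Conclusion.** The point holds as a mismatch between one stated aim and the design. The Protocol sets out to determine whether EmoLED is no worse on adverse events, yet the trial is a superiority pilot of 20 per arm with a descriptive safety analysis, and it cannot support that conclusion. Even the most favourable result, no events in either arm, leaves a difference of about 16 points compatible with the data; with 4/20 in both arms it is about 25 points.

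The bound for 0/20 depends only on the arm size. The other scenarios rest on assumed counts, rates and margins, but the conclusion is the same across the range tried.

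Severity is modest. Safety is a secondary endpoint, no calculation in the Protocol is wrong, and nothing here suggests that the device is unsafe.

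**What to change.** 1. In Study Objectives, replace the safety clause with an aim of describing adverse events by arm, which matches the secondary endpoint and the Statistical analysis section.
2. Report the number and proportion of patients with at least one adverse event per arm, and the difference with its 95% interval, alongside the count of events. This may be placed in the statistical analysis plan.
3. State that no conclusion that EmoLED is at least as safe as standard therapy will be drawn from this pilot.

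No extra patients, visits or data are needed, because adverse events are already recorded on each patient's data collection form. The cost is wording, through the Protocol's amendment procedure where that applies, and a less favourable safety claim. Keeping the aim as written would instead mean fixing a margin in advance and sizing the trial for it, which on the assumptions above is well beyond 20 per arm unless the margin is very wide.

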### **Ethical considerations**

This Study will be conducted with reference to the standards of Good Clinical Practice and in accordance with the principles of the Declaration of Helsinki, with the UNI\_ISO\_14155\_2011 norm, and with all relevant local laws and regulations, applicable to clinical trials that use patients as research object. This clinical investigation cannot begin in the various centers involved before having received the favorable written approval of the Ethics Committee of the coordinating center and the respective Ethics Committees. The medical assistance provided to the subject is responsibility of adequately qualified doctors, as all the centers involved in this

study are specialized in the treatment of the pathology object of the clinical trial (Diabetology units or Diabetic Foot clinics).

During this trial, the patients' right to physical and mental integrity, the right to privacy and the protection of data concerning them will be respected in accordance with Directive 95/46/EC.

This clinical investigation was designed to cause as little pain, discomfort, fear and other foreseeable risks for the subject as possible, and the degree of discomfort related to the trial itself or to the treatment with the medical device in question is almost nil, considering the Clinical Evaluation Report of the device and the safety data obtained from post-marketing surveillance.

The degree of discomfort/pain of the enrolled patients is however subject to continuous verification during the clinical trial, through a special questionnaire on the detection of discomfort connected to participating in the study in question. The risk/benefit ratio will be constantly checked throughout the trial, taking into account any adverse events/device-related accidents or non-serious side effects reported by the main investigators, and the preliminary assessment of the benefits about patients who have completed the study process.

The principal investigator (PI) of each center is responsible for an adequate management of the study of their own center and for the coordination of the personnel involved. The PI must be responsible for all medical decisions regarding the study and ensure that adequate medical assistance is provided to the subject in case of any adverse event. The investigator should conduct the study in accordance with the protocol agreed with the sponsor and the authorities.

